| NCI-CTCAE | National Cancer Institute – Common Terminology Criteria for Adverse Events |

| | |
|------------------|---|
| OR | Odds Ratio |
| PaO ₂ | Arterial Oxygen Partial Pressure |
| CCI | |
| PT | Preferred Term |
| PK | Pharmacokinetic(s) |
| SAE | Serious Adverse Event |
| SARS-CoV-2 | Severe Acute Respiratory Syndrome Coronavirus 2 |
| SD | Standard Deviation |
| SDTM | Study Data Tabulation Model |
| SOC | System Organ Class |
| SpO ₂ | Peripheral Capillary Oxygen Saturation |
| TEAE | Treatment-Emergent Adverse Event |
| t _{max} | Time to Maximum Concentration |
| WHO-DD | World Health Organization Drug Dictionary |

3 Modification History

| Unique Identifier for Version | Date of IAP Version | Author | Changes from the Previous Version |
|-------------------------------|---------------------|--------|---|
| 1.0 | 08-AUG-2020 | PPD | Not applicable, as first version. |
| 2.0 | 29-APR-2021 | PPD | 
Primary efficacy endpoint was changed.
 
Intent-To-Treat Analysis Set and Safety Analysis Set definitions were updated.
 
Subgroup selection and analysis per subgroups were updated.
 
Additional imputation rules for missing data were added.
 
Analysis visits were described.
 
Subject disposition analysis was updated.
 
Censoring rules for time-to-event analysis were updated.
 
Inclusion of stratification factors to the models was updated.
 
Time to hospital discharge analysis was added.
 
Sensitivity analysis was kept only for the primary efficacy endpoint.
 
Randomization date/time was replaced with first dose date/time for all duration and time-to calculations.
 
Appendix 2 was removed.
 |

4 Purpose of the Integrated Analysis Plan

The purpose of this Integrated Analysis Plan (IAP) is to document technical and detailed specifications for the analysis of data collected for protocol MS200569-0026 (ANEMONE). Results of the analyses described in this IAP will be included in the Clinical Study Report (CSR).

CCI
 Additionally, the planned analyses identified in this IAP may be included in regulatory submissions or future manuscripts. Any post-hoc, or unplanned analyses performed to provide results for inclusion in the CSR but not identified in this prospective IAP will be clearly identified in the CSR.

The IAP is based upon Section 10 (Statistical Considerations) of the study protocol and is prepared in compliance with ICH E9. Details of the IDMC analyses of the participants' safety and PK are also described. The first version of this IAP was finalized before the first IDMC data review meeting, scheduled once the first 15 patients complete their 14-day treatment period. The current version of the IAP incorporates changes resulting from protocol amendments as described in protocol version 4.0 dated 01 March 2021, notably the change of primary endpoint.

5 Objectives and Endpoints

5.1 Part A Objectives

Part A objectives will be separately described only in case of early termination of the study for safety reasons before the start of Part B, otherwise all data from all study participants from Part A and Part B will be combined.

| OBJECTIVES | ENDPOINTS (OUTCOME MEASURES) | IAP SECTIONS |
|---|---|---|
| Primary | | |
| To assess the safety of M5049 compared to placebo. | 
 Incidence of TEAEs, AESIs, TEAEs leading to treatment discontinuation, and SAEs from Day 1 through Day 60. Clinically significant changes in laboratory parameters and ECGs from Day 1 through Day 28. | 
 15.1 15.3 and 15.5 |
| Secondary | | |
| To evaluate clinical deterioration with M5049 compared to placebo. | 
 Time to ICU (Day 1 through Day 28). Time to invasive mechanical ventilation (Day 1 through Day 28). | 
 14.2.5 14.2.7 |
| To evaluate the change in clinical status with M5049 compared to placebo. | Clinical status from Day 1 through Day 60 (on a 9-point ordinal scale): 
 Uninfected: no clinical or virological evidence of infection. Ambulatory: no limitation of activities. | 14.2.2 |

| OBJECTIVES | ENDPOINTS (OUTCOME MEASURES) | IAP SECTIONS |
|----------------------------|--|--------------|
| | 
 2. Ambulatory: limitation of activities. 3. Hospitalized, mild disease: hospitalized, no oxygen therapy. 4. Hospitalized, mild disease: oxygen by mask or nasal prongs. 5. Hospitalized, severe disease: noninvasive ventilation or high flow-oxygen. 6. Hospitalized, severe disease: intubation and mechanical ventilation. 7. Hospitalized, severe disease: ventilation + additional organ support – e.g., pressors, RRT, ECMO. 8. Death. | |
| To assess the PK of M5049. | Pharmacokinetic parameters: C_{max} , t_{max} , λ_z , $t_{1/2}$, $AUC_{0-tlast}$, AUC_{0-12h} , $AUC_{0-\infty}$, CL/F , V_z/F , C_{max}/D , $AUC_{0-tlast}/D$, AUC_{0-12h}/D , $AUC_{0-\infty}/D$, $R_{acc}(AUC_{0-12h})$, $R_{acc}(C_{max})$ on Day 1 and Day 7.. | 16.1 |

AESI = adverse event of special interest; CL/F = apparent total body clearance of study intervention following extravascular administration; ECG = electrocardiogram; ECMO = extracorporeal membrane oxygenation; IAP = Integrated Analysis Plan; ICU = intensive care unit; λ_z = elimination rate constant; PK = pharmacokinetic; RRT = rapid response team; SAE = serious adverse event; TEAE = treatment-emergent adverse event; V_z/F = apparent volume of distribution.

5.2 Part B Objectives

| OBJECTIVES | ENDPOINTS (OUTCOME MEASURES) | IAP SECTIONS |
|---|--|---|
| Primary Efficacy | | |
| To evaluate the time to recovery in participants hospitalized due to COVID-19 pneumonia with M5049 compared to placebo. | Time to recovery from Day 1 through Day 28, defined as time from Day 1 to first occurrence of WHO 9-point ordinal scale 3 or less. | 14.1 |
| Primary Safety | | |
| To assess the safety of M5049 compared to placebo. | 
 Incidence of TEAEs, AESIs, TEAEs leading to treatment discontinuation, and SAEs from Day 1 through Day 60. Clinically significant changes in laboratory parameters and ECGs from Day 1 through Day 28. | 
 15.1 15.3 and 15.5 |
| Secondary | | |
| To assess the proportion of participants free of respiratory support with M5049 compared to placebo. | Alive and not requiring supplemental oxygenation (including any supplemental oxygen, noninvasive or mechanical ventilation and ECMO) through Day 28. | 14.2.1 |
| To evaluate the change in clinical status with M5049 compared to placebo. | 
Clinical status from Day 1 through Day 60 (on a 9-point ordinal scale):
 
 0. Uninfected: no clinical or virological evidence of infection. 1. Ambulatory: no limitation of activities. 2. Ambulatory: limitation of activities. 3. Hospitalized, mild disease: hospitalized, no oxygen therapy. 4. Hospitalized, mild disease: oxygen by mask or nasal prongs. 5. Hospitalized, severe disease: noninvasive ventilation or high flow-oxygen. 6. Hospitalized, severe disease: intubation and mechanical ventilation. 7. Hospitalized, severe disease: ventilation + additional organ support – e.g., pressors, RRT, ECMO. 8. Death. | 14.2.2 |
| To assess normalization of oxygenation status with M5049 compared to placebo in participants who are alive and not on mechanical ventilation. | 
Time to SpO₂ of ≥ 94% sustained for at least 24 hours in room air from Day 1 through Day 28.
 
Further referred as “time to SpO₂ improvement”
 | 14.2.3 |

| OBJECTIVES | ENDPOINTS (OUTCOME MEASURES) | IAP SECTIONS |
|---|--|--|
| To evaluate the numbers of deaths with M5049 compared to placebo. | All-cause mortality (Day 1 through Day 60). | 14.2.4 |
| To evaluate clinical deterioration with M5049 compared to placebo. | 
 • Time to ICU (Day 1 through Day 28). • Time to invasive mechanical ventilation (Day 1 through Day 28). • Time to noninvasive mechanical ventilation (Day 1 through Day 28). | 
 • 14.2.5 • 14.2.7 • 14.2.6 |
| To assess the length of stay in the ICU with M5049 compared to placebo. | Total days in ICU from Day 1 through Day 60. | 14.2.8 |
| To assess the length of hospital, stay with M5049 compared to placebo. | 
 • Total days in the hospital from Day 1 through Day 60. • Time to hospital discharge from Day 1 to Day 28 | 14.2.9 |
| To evaluate modulation of biomarkers of COVID-19 inflammation with M5049 compared to placebo. | Inflammatory biomarkers (CRP, d-dimer, and ferritin) during study period (Day 1 through Day 28). | 14.2.10 |
| To evaluate modulation of select biomarkers with M5049 compared to placebo. | Biomarkers (IL-6, TNF alpha, IL-8) during study period (Day 1 through Day 28). | 14.2.11 |
| To evaluate occurrence of relapse with M5049 compared to placebo. | Occurrence of relapse in participants during the study period (if first discharged within the 60-day study period). Relapse refers to worsening oxygenation, with either a positive result of any respiratory pathogenic nucleic acid test, or worsening lesions on chest imaging with re-hospitalization. | 14.2.12 |
| To assess occurrence of re-hospitalizations due to COVID-19 disease complications. | Occurrence of re-hospitalization in participants during the study period (if first discharged within the 60-day study period) due to COVID-19 disease complications (Day 5 through Day 60). | 14.2.13 |

AESI = adverse event of special interest; COVID-19 = coronavirus disease 2019; CRP = C-reactive protein; C_{trough} = predose observed concentration; ECG = electrocardiogram; ECMO = extracorporeal membrane oxygenation; IAP = Integrated Analysis Plan; ICU = intensive care unit; IFN = interferon; CCI [REDACTED]; PK = pharmacokinetic; CCI [REDACTED] RRT = rapid response team; SAE = serious adverse event; SARS-CoV = severe acute respiratory syndrome coronavirus; SpO₂ = peripheral capillary oxygen saturation; TEAE = treatment-emergent adverse event; CCI [REDACTED]

6 Overview of Planned Analyses

All statistical analyses, with the exception of listings provided for internal Independent Data Monitoring Committee (IDMC) meeting 1, will be performed on the basis of CDISC SDTM data, used as source for CDISC ADaM data creation. These SDTM data contain as clean as possible eCRF data as well as external data including pharmacokinetics (PK) data CCI [REDACTED] CCI [REDACTED]

6.1 Analyses for IDMC meeting 1

The IDMC meeting 1 was held to assess the safety of the investigational treatment, to safeguard the interests of study participants and to monitor the overall conduct of the clinical study.

Once all Part A participants completed the 14 days treatment period or discontinued from study prematurely, a data snapshot of as clean as possible eCRF data was taken for provision of IDMC outputs. The data cut-off was the date of data snapshot.

The IDMC was provided with a subset of partially unblinded safety data using group-level masking. The data included demographics, adverse events, deaths, ICU admission, use of mechanical ventilation.

Pooled dose-normalized PK summary statistics across dose groups was provided to the IDMC CCI [REDACTED]

CCI [REDACTED]

Further details on the full membership, mandate, and processes, analyses and data handling for IDMC are presented in the documents listed below:

- IDMC Charter and appendices
- Listings for IDMC1 meeting (shells)
- Unblinding Plan

6.2 Analyses for subsequent IDMC Meetings

Additional IDMC meetings were held to review accumulating safety data as defined in the Clinical Study Protocol (CSP) and to monitor the overall conduct of the clinical study. Blinded and partially blinded outputs were created to support IDMC safety review based on the list reported in the “MS200569_0026_TOC_Section15” Excel document.

6.3 Final Analysis

This analysis will be the main analysis. All planned analyses identified in the study protocol and in this IAP will be performed only after the last participant has completed the safety follow up period with all study data in-house, and the database will be locked for the analysis.

A data review meeting will be held prior to any database lock.

7 Changes to the Planned Analyses in the Clinical Study Protocol

The inclusion of all stratification factors is identified as a potential source of problems in the implementation and interpretation of statistical models used to analyze efficacy. For this, use of corticosteroids before randomization and country will only be included, as deemed the most relevant factors, while presence of obstructive lung disease and use of antiviral therapy before randomization will be analyzed as subgroups.

8 Analysis Populations and Subgroups

8.1 Definition of Analysis Populations

The analysis populations are specified below. The final decision to exclude participants from any analysis population will be made during a data review meeting prior to database lock and unblinding.

Enrolled Analysis Set

The Enrolled Analysis Set includes all participants who sign informed consent and will be used to report disposition data.

Intent-To-Treat Analysis Set (ITT)

The ITT consists of all treated participants and it will be used for the primary efficacy analysis.

Participants will be analyzed according to the actual treatment received, which will be determined based on the treatment taken just after randomization, as collected in the electronic Case Report Form (eCRF). Occurrences of mistreatment (i.e. a different treatment from the one assigned via randomization) will be evaluated on a case by case basis.

Safety Analysis Set (SAF)

The SAF consists of all participants who received at least one dose of study intervention and is used for evaluation of safety endpoints.

Participants will be analyzed according to the actual treatment received, which will be determined based on the treatment taken just after randomization, as collected in the eCRF. Occurrences of mistreatment will be evaluated on a case by case basis.

Therefore, the ITT and the SAF are the same population and can be used interchangeably.

Pharmacokinetics Analysis Set (PKAS)

The PKAS will include all participants who received at least one dose of active treatment, for whom at least one quantifiable post dose plasma concentration of M5049 is obtained, and without any relevant protocol deviations and absence of factor that may have an influence on PK. It will be used for the evaluation of PK endpoints.

Participants will be analyzed according to the actual treatment received, which will be determined based on the treatment taken just after randomization, as collected in the eCRF. Occurrences of mistreatment will be evaluated on a case by case basis.

Pharmacodynamics Analysis Set (PDAS)

The PDAS will include all participants who received at least one dose of study intervention, for whom at least one post-baseline biomarker result is obtained and without any relevant protocol deviations or events that may have an influence on pharmacodynamics. It will be used for the evaluation of endpoints related to inflammatory and CCI biomarkers.

Participants will be analyzed according to the actual treatment received, which will be determined based on the treatment taken just after randomization, as collected in the eCRF. Occurrences of mistreatment will be evaluated on a case by case basis.

Analyses per Analysis Sets

The following table summarizes the use of the analysis sets in the different analyses.

| Analyses | Analysis Sets | | |
|------------------------------------|---------------|------|------|
| | ITT/SAF | PKAS | PDAS |
| Baseline Characteristics | ✓ | | |
| Previous and Concomitant Therapies | ✓ | | |
| Compliance and Exposure | ✓ | | |
| Efficacy: Primary | ✓ | | |
| Other Efficacy | ✓ | | |
| Inflammatory CCI Biomarkers | | | ✓ |
| Pharmacokinetics | | ✓ | |
| Safety | ✓ | | |

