7.4.1 Corticosteroids

Corticosteroids should not be initiated or their dose changed once the participant has entered the study so as to not interfere with the primary objective of this study - evaluation of the anti-inflammatory effects of the study drug.

Corticosteroids initiated prior to or during the study Screening period (and prior to randomization) must not be higher than 40 mg prednisone per day based on the dosing regimen and schedule used in the RECOVERY Trial (NCT04381936) performed by the University of Oxford, United Kingdom ([Horby 2002](#)). The corticosteroid dosing (6 mg of dexamethasone, \leq 40 mg prednisone, refer to [Table 3](#)) schedule must be completed within 10 days of corticosteroids initiation as per the RECOVERY Trial (mean days of corticosteroid use was 6 days).

Table 3 Prednisone Equivalence Calculation (Total Daily Dose)

Oral Corticosteroid Medication	Equivalent (mg) to 1 mg Prednisone	Equivalent (mg) to 15 mg Prednisone ^a	Maximum allowed daily dose (mg)
Betamethasone	0.15	2.3	6
Cortisone	5	75	200
Deflazacort	1.2	18	48
Dexamethasone	0.15	2.3	6
Hydrocortisone	4	60	160
Meprednisone	0.8	12	32
Methylprednisolone	0.8	12	32
Prednisolone	1	15	40
Triamcinolone	0.8	12	32

^a In Part B, participants will be stratified based on the use of corticosteroids within 48 hours prior to randomization: prednisone equivalent daily dose of ≤ 15 mg or > 15 mg.

However, if the participant requires invasive mechanical ventilation AND the hospital standard of care recommends use of corticosteroids (up to 40 mg prednisone-equivalent daily) and/or other anti-inflammatory medications, these drugs will be permitted. Any additional anti-inflammatory use initiated at the same time of mechanical ventilation should also be recorded, i.e., the name, reason for use, dates administered, and dosing information.

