10.3 Populations for Analyses

The analysis populations are specified below. The final decision to exclude participants from any analysis population will be made during a blinded data review meeting prior to database lock and unblinding.

Analysis Set	Description
Enrolled	All participants who sign informed consent.
Intent-to-Treat	The Intent-to-Treat Analysis Set consists of all treated participants. Participants will be analyzed according to the actual treatment received. The Intent-to-Treat Analysis Set will be used for the primary efficacy analysis.
Safety	The Safety Analysis Set consists of all participants who receive at least one dose of study intervention and is used for evaluation of safety endpoints. Participants will be analyzed according to the actual treatment they receive.
Pharmacokinetics	The Pharmacokinetic Analysis population will include all participants who received at least 1 dose of active treatment, for whom at least 1 quantifiable plasma concentration of M5049 is obtained, and without any relevant protocol deviations and absence of factor that may have an influence on pharmacokinetics.
Pharmacodynamics	The Pharmacodynamic Analysis population will include all participants who received at least 1 dose of study intervention, for whom at least 1 postbaseline biomarker assessment was obtained and without any relevant protocol deviations or event that may have an influence on pharmacodynamics.

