14.2.10 Inflammatory Biomarkers

Inflammatory biomarker analysis will be based on data collected on the ‘Inflammatory biomarkers’ eCRF page and will be performed based on the PDAS.

The following inflammatory biomarkers will be collected for this study and analyzed by a local laboratory as per the schedule of events reported in the protocol:

- C-Reactive Protein, D-dimer, Ferritin

The following summaries will be provided by treatment group and total based on the PDAS for each inflammatory biomarker:

- Observed, change and percent change from baseline by analysis visit;
- Box and whisker plots over time for observed, change and percent change from baseline by treatment group;
- Spaghetti plots of change and percent change from baseline by treatment group

CCI

CCI

CCI

CCI

CCI

CCI

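### The pharmacodynamic set for CRP, D-dimer and ferritin can drop whole participants for undefined post-randomisation events, and no all-treated summary stands beside it

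*SAP*

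**What the plan says.** SAP 8.1 builds the PDAS from participants who took at least one dose, have at least one post-baseline biomarker result, and are "without any relevant protocol deviations or events that may have an influence on pharmacodynamics". Protocol 10.3 has nearly identical wording: "without any relevant protocol deviations or event that may have an influence on pharmacodynamics". Neither document says which deviations are relevant, which events qualify, or when they must occur.

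SAP 8.1 also gives the purpose of the set, with one word redacted: "It will be used for the evaluation of endpoints related to inflammatory and CCI biomarkers". In the table of analysis sets that follows, the biomarker row is ticked for PDAS alone, while the primary and other efficacy rows use ITT/SAF. SAP 14.2.10 repeats the choice for CRP, D-dimer and ferritin: the analysis is taken from the "eCRF page and will be performed based on the PDAS".

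The objective served is a Part B secondary objective (SAP 5.2): "To evaluate modulation of biomarkers of COVID-19 inflammation with M5049 compared to placebo". A parallel objective covers IL-6, TNF alpha and IL-8, but its analysis section (SAP 14.2.11) is redacted.

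Protocol 7.4.1 bars starting or changing corticosteroids after entry, with one exception. If a participant needs invasive ventilation and hospital practice recommends corticosteroids "and/or other anti-inflammatory medications, these drugs will be permitted". Protocol 7.4.2 says hemoperfusion could lower IL-6, Type I IFN or TNF alpha and would confound the outcome.

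**The concern.** A comparison of randomised arms stays protected when membership of the analysis set does not depend on what happens after treatment starts. Here it can. A participant who worsens may receive a drug or procedure that acts on inflammation. That treatment can then be judged an event influencing pharmacodynamics, or, if steroids were started outside the permitted exception, a deviation. Either route removes the participant and every sample they gave.

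If M5049 changes how often participants worsen, the arms lose different numbers, and those lost need not resemble those kept. The by-arm biomarker summaries then describe participants who stayed free of such events, a group that treatment may itself have shaped.

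This matters even in an exploratory trial. Protocol 4.3 justifies both doses partly by the chance of seeing inflammatory biomarkers suppressed, and these by-arm summaries are where a reader will look for that.

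**Working it through.** The visible documents give no effect size, standard deviation or exclusion rate for biomarkers, so there is no planned figure to reproduce. The check is of the text, followed by arithmetic on assumed inputs.

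**Text check**

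- *Unit of exclusion.* Under SAP 8.1 it is the participant. By contrast, SAP 16.1 lets individual erroneous PK concentrations be set aside. The visible pharmacodynamic text has no sample-level rule. CRP, D-dimer and ferritin are scheduled at Screening and on Days 1, 3, 7, 10, 14 and 28 (Protocol 1.2), so an event on Day 8, say, could cost valid Day 3 and Day 7 results.
- *Timing.* There is no pre-randomisation limit in SAP 8.1 or Protocol 10.3.
- *Foreseeable events.* Anti-inflammatory drugs on invasive ventilation (Protocol 7.4.1) and hemoperfusion (7.4.2). Protocol 10.4.2 already treats ICU admission, invasive ventilation, corticosteroids and forbidden medication as intercurrent events for the primary endpoint. No such handling is visible for biomarkers.
- *Back-up analysis.* None is visible for CRP, D-dimer and ferritin. SAP Section 3 records that sensitivity analysis was kept only for the primary efficacy endpoint.

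**How exclusion moves a difference in means**

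Let p be the share of an arm excluded and D the mean of those excluded minus the mean of those kept, on whatever scale is summarised. Then:

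all-treated mean = PDAS mean + p × D

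With P for placebo and A for M5049:

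(PDAS difference, A minus P) − (all-treated difference, A minus P) = pP × DP − pA × DA

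This is zero when p × D is equal in the two arms. Its sign depends on D as well as p. If those excluded have higher values and placebo loses more, the shift is against M5049. If rescue has lowered their later values, D can be negative and the shift reverses.

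**Illustration (all inputs assumed except the arm size)**

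Arm size: 150 / 3 = 50 (Protocol 4.1, 1:1:1 allocation). Suppose M5049 acts only by preventing worsening, everyone who worsens is excluded, and D is the same in both arms on the log scale. The PDAS ratio is then 1.00, and the all-treated ratio is exp((pA − pP) × D):

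| Excluded, placebo vs M5049 | Participants of 50 | D = 0.5 | D = 1.5 |
|---|---|---|---|
| 10% vs 10% | 5 vs 5 | 1.00 | 1.00 |
| 10% vs 5% | 5 vs 2.5 | exp(−0.025) = 0.975 | exp(−0.075) = 0.928 |
| 20% vs 10% | 10 vs 5 | exp(−0.05) = 0.951 | exp(−0.15) = 0.861 |

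With D = 1.5 the distortion factor is exp(0.075) = 1.08 in the second row and exp(0.15) = 1.16 in the third. Reversing the sign of D gives exp(−0.075) = 0.93 and exp(−0.15) = 0.86.

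A second model assumes no true marker difference and removes the worst share of each arm on a latent severity with correlation r to the marker. The PDAS difference is r × [t(pA) − t(pP)], where t(p) = −φ(z)/(1 − p), φ is the standard normal density and z is the 1 − p normal quantile. For 20% versus 10%, t is −0.350 and −0.195, so the spurious difference is 0.155 × r: about 0.05 SD at r = 0.3 and 0.11 SD at r = 0.7.

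**The case against.** The strongest reply is that the rule names no events. It does not say that rescue anti-inflammatories, infection or stopping study drug lead to exclusion. Rescue on invasive ventilation is permitted, so it is not in itself a deviation. On-study hemoperfusion is prohibited and should be rare. A reader might infer that participants who worsen will be removed in proportion to how often each arm deteriorates; the documents do not establish that. This stands: exclusion is possible and left to judgement.

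Second, a reader might take 1.08 to 1.16 as the expected bias. It is not. The exclusion rates and D are assumed, and the visible plan produces no geometric-mean ratio. It gives observed values, change and percent change by arm, with plots (SAP 14.2.10); SAP 9.2.2 specifies geometric means for PK parameters only. On change from baseline the gap between those excluded and those kept could be smaller.

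Third, direction. Rescue may lower later values. Separately, results are recorded unless the participant has been discharged, so missing data remove those who recover and pull the other way. This also stands.

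Fourth, a reader might fault the PDAS for requiring a post-baseline result. That is not a defect of this set: any summary of change needs one, and losses after early discharge are a sampling limit that no analysis set repairs.

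Fifth, there are safeguards. Exclusions are decided before unblinding, at a meeting Protocol 10.3 calls blinded, and SAP 10.2.2 lists the reasons. Blinding prevents choices driven by knowledge of the arm. It does not prevent selection on an outcome that treatment has changed. The listing makes the exclusions visible but returns no data.

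Finally, the trial is exploratory with no formal hypothesis testing (SAP Section 9), and an all-treated summary mixes drug and rescue effects. Which summary is called main is partly a choice of question. That argues for showing both, not for showing the PDAS alone.

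**Conclusion.** The concern holds in a limited form. An undefined, participant-level exclusion rule that can act on post-randomisation events governs the only visible analysis set for the CRP, D-dimer and ferritin comparison with placebo. Blinded review and a listing of reasons do not remove that weakness.

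The documents do not fix its size or direction. It is zero if qualifying events, and the marker profiles of those who have them, are the same in each arm. Under the assumed inputs above, losing 10 placebo and 5 M5049 participants could hide an all-treated ratio of 0.86 to 0.95. That is an illustration only.

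For IL-6, TNF alpha and IL-8 the point is less secure, because the redacted section may already contain a further analysis. The primary endpoint is not affected, since it uses the all-treated set. The change is worth making because it is cheap and gives a comparison less open to selection.

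**What to change.** 1. Produce the CRP, D-dimer and ferritin summaries in SAP 14.2.10 on all treated participants with a baseline and any post-baseline result, beside the PDAS version. Do the same for the serum biomarkers if the redacted section does not already do so.
2. In the PDAS, exclude only samples taken after the influencing event and keep the participant's earlier samples.
3. List in SAP 8.1, before unblinding, the deviations and events that qualify.
4. Replace the bare listing in SAP 10.2.2 with a table of exclusions by arm and reason, keeping the listing as support.
5. Record the sample-level rule in SAP Section 7, because it departs from the definition in Protocol 10.3.

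Cost: SAP wording and one repeat of the biomarker outputs, with no new data and no change to participant care. Downside: the all-treated summary includes values after rescue, which may add variability and mix drug and rescue effects. The PDAS output shown beside it covers this.
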